### **7.1.2 Efficacy Evaluable Population for PFS – PFS Evaluable Analysis Set**

All patients who receive at least one dose of any study-specific treatment (CB-839 or nivolumab) will be included in the analysis of safety. The PFS analysis will be performed by cohort.

### **7.1.3 Safety Analysis Set**

All patients who receive at least 1 dose of any study-specific treatment (CB-839 or nivolumab) will be included in the analysis of safety. All safety analyses will be performed by cohort.

## **7.2 Analysis of Study Conduct**

Subject disposition, including enrollment, analysis populations, reason for discontinuation from the study, and on-study status will be summarized by cohort and overall for the safety analysis set. Protocol deviations are not collected in the case report form but entered manually and provided by electronic data transfer. If protocol deviations are sufficiently standardized to allow summarization, major protocol deviations (including major deviations of inclusion and/or exclusion criteria) will be summarized. Protocol deviations will be listed regardless of the level of standardization.

## **7.3 Analysis of Treatment Group Comparability**

Demographic and baseline characteristics, including age, sex, race, ethnicity, and disease characteristics will be summarized by cohort and overall for the safety analysis set.

Baseline values are defined as the last available data obtained prior to the patient receiving the first dose of any study treatments on Cycle 1 Day 1 visits unless otherwise noted.

## **7.4 Efficacy Analysis**

Efficacy analyses will be performed by cohort. Response to treatment will be evaluated per Investigator assessed using RECIST v1.1.

The cohorts are based on patient's tumor type instead of randomization, therefore formal hypothesis testing among cohorts will not be performed.

### **7.4.1 Primary Analysis of Overall Response Rate**

Overall Response Rate (ORR) will be assessed by cohort where ORR is defined as the percentage of patients with complete response (CR) or partial response (PR) per Response Evaluation Criteria in Solid Tumors (RECIST) v1.1. To be assigned a status of CR or PR, changes in tumor measurements must be confirmed by repeat assessment performed no less than 4 weeks after the criteria for response were first met. Patients without assessed response will be treated as non-responders.

The analysis set for ORR will be the response evaluable analysis set. An estimate of ORR and its 95% CI will be calculated with the Clopper-Pearson method. Best Overall Response (BOR) Rate is defined as the percentage of patients with their best of response being will be estimated in the same approach as for ORR.

Duration of Response (DOR): For patients achieving a PR or a CR, the duration of response will be calculated as the time between the first documentation of a PR or a CR to the first documentation of PD or death, whichever occurs first. For patients achieving first a PR then a CR, the PR date will be the starting date for response duration calculation. Patients who are alive and have not experienced disease progression at the time of the analysis will follow the censoring rules in [Table 2](#) where only assessments after first response will be included. The determination of DOR is based on responders only.

Kaplan-Meier methodology will be used to estimate median DOR for each cohort and construct survival curves for visual description. The Brookmeyer-Crowley methodology will be used to construct the 95% CI for the median DOR for each cohort (2). DOR will be analyzed using response evaluable analysis set.

DOR will be reported for patients with confirmed OR.

#### 7.4.2 *Secondary Analyses*

Progression Free Survival: PFS is defined as time from the first dose date to the earlier of either progression of disease per RECIST 1.1 or death from any cause. If the disease progression assessment involves more than one date, the earliest date will be used as the event date.

The duration of PFS will be censored at the date of the last radiographic disease assessment if:

- Patient is alive and progression free at the time of analysis data cutoff.
- Disease progression or death occurs after missing data (including an inevaluable status for overall response assessment) for two consecutive radiographic disease assessments.
- Patient receives non-protocol treatment prior to documentation of disease progression.

Patients missing baseline disease assessment will be censored at the first dose date (C1D1). Patients who come off of study for reason other than PD or death should continue to be followed with radiographic assessment until PD by RECIST 1.1, death, withdrawal of consent, or initiation of another systemic anti-cancer treatment. Censoring rules are summarized in [Table 2](#)

The analysis set for PFS will be the PFS evaluable analysis set. Kaplan-Meier methodology will be used to estimate median PFS for each cohort and construct survival curves for visual description. The Brookmeyer-Crowley methodology will be used to construct the 95% CI for the median PFS for each cohort (2).

Overall Survival (OS): OS is defined as the time from the first dose date to death due to any cause. For patients alive at time of analysis, OS will be censored at the time when the

patient is last known to be alive. Patients who discontinue study for reason other than death should continue to be followed for survival status until death or withdrawal of consent. Because OS may require longer follow up than the primary PFS analysis, additional OS analyses may be performed after the time of PFS primary analysis. OS will be analyzed with the same methodologies and analysis set as PFS.

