**6.0 CORE PROTOCOL****6.1 Objectives**

Primary Objectives	Primary Endpoints
To evaluate the safety and tolerability of CB-839 in combination with nivolumab for patients with advanced/metastatic clear cell Renal Cell Carcinoma (ccRCC), melanoma (MEL), and Non-Small Cell Lung Cancer (NSCLC)	Evaluation of clinical tolerability of CB-839 in combination with nivolumab, including dose intensity of CB-839, adverse events, and laboratory data
To evaluate anti-tumor effect of CB-839 in combination with nivolumab for patients with advanced/metastatic ccRCC, MEL, and NSCLC as assessed by investigator	Overall response rate (ORR) and duration of response (DOR) per Investigator assessed Response Evaluation Criteria in Solid Tumors (RECIST) v1.1
To evaluate anti-tumor effect of CB-839 in combination with nivolumab for patients with advanced/metastatic MEL by Independent Radiology Committee (IRC)	Overall response rate (ORR) and duration of response (DOR) by Independent Radiology Committee (IRC)-assessed Response Evaluation Criteria in Solid Tumors (RECIST) v1.1
Secondary Objectives	Secondary Endpoints
To select the recommended Phase 2 dose (RP2D) of CB-839 in combination with nivolumab for patients with advanced/metastatic ccRCC, MEL, and NSCLC	Based on an evaluation of adverse events, pharmacokinetics, pharmacodynamics and evidence of clinical activity
To evaluate the progression-free survival (PFS) and overall survival (OS) of CB-839 in combination with nivolumab for patients with advanced/metastatic ccRCC, MEL, and NSCLC by standard RECIST criteria	Assessed by progression-free survival (PFS) per RECIST v1.1 and overall survival (OS)
To evaluate anti-tumor effect of CB-839 as monotherapy in patients with advanced/metastatic MEL	Assessed by ORR, DOR and PFS per RECIST v1.1
Determine pharmacokinetics (PK) of CB-839 in combination with nivolumab	Non-compartmental method of analysis will be used to analyze the plasma concentrations of CB-839
Exploratory Objectives	Exploratory Endpoints
To evaluate the pharmacodynamic effects of CB-839 alone and in combination with nivolumab in patients with advanced/metastatic ccRCC, MEL, and NSCLC	To include evaluation of changes in peripheral blood immunophenotyping, tumor immune infiltrate and plasma glutamine levels

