## 16.5 Efficacy Analysis

For the primary efficacy analysis, response to treatment will be evaluated by RECIST v1.1. For all cohorts except for Cohort 4, the primary endpoint will be investigator-assessed, while for Cohort 4 the primary endpoint will be IRC assessed.

The Kaplan-Meier method will be used to estimate the median Duration of Response (DOR), Progression-Free Survival (PFS), and overall survival (OS) for each treatment cohort in Dose Expansion.

- ORR is defined as the percentage of patients with complete response (CR) or partial response (PR) according to the RECIST 1.1 criteria. Response confirmation is required a minimum of 4 weeks after the date of the initial determination of response.
- DOR is defined as the number of days from the date of initial response (PR or better) to the date of first documented disease progression/relapse or death, whichever occurs first.
- PFS is defined as the number of days from the date of treatment initiation (i.e., C1D1) to the date of documented disease progression (radiographic or clinical) or death from any cause, whichever occurs first, and will be calculated for all patients who receive at least one dose of study treatment. In the event that no disease progression or death is documented prior to study termination, analysis cutoff, or the start of confounding anticancer therapy, these endpoints will be censored at the date of last available tumor assessment.
- OS is defined as the number of days from the date of treatment initiation (i.e., Cycle 1 Day 1) to the date of death from any cause and will be calculated for all patients who receive at least one dose of treatment. In the event that no death is documented prior to study termination or analysis cutoff, OS will be censored at the last date the patient is known to be alive.

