### Special notes on response assessment

When nodal disease is included in the sum of target lesions and the nodes decrease to 'normal' size (< 10 mm), they may still have a measurement reported on scans. This measurement should be recorded even though the nodes are normal in order not to overstate progression should it be

based on increase in size of the nodes. As noted earlier, this means that patients with CR may not have a total sum of ‘zero’ on the case report form (CRF).

In trials where confirmation of response is required, repeated ‘NE’ time point assessments may complicate best response determination. The analysis plan for the trial must address how missing data/assessments will be addressed in determination of response and progression. For example, in most trials it is reasonable to consider a patient with time point responses of PR-NE-PR as a confirmed response.

Patients with a global deterioration of health status requiring discontinuation of treatment without objective evidence of disease progression at that time should be reported as ‘symptomatic deterioration’. Every effort should be made to document objective progression even after discontinuation of treatment. Symptomatic deterioration is not a descriptor of an objective response: it is a reason for stopping study therapy. The objective response status of such patients is to be determined by evaluation of target and non-target disease.

Conditions that define ‘early progression, early death, and non-evaluability are study specific and should be clearly described in each protocol (depending on treatment duration, treatment periodicity).

In some circumstances it may be difficult to distinguish residual disease from normal tissue. When the evaluation of complete response depends upon this determination, it is recommended that the residual lesion be investigated (fine needle aspirate/biopsy) before assigning a status of complete response. FDG-PET may be used to upgrade a response to a CR in a manner similar to a biopsy in cases where a residual radiographic abnormality is thought to represent fibrosis or scarring. The use of FDG-PET in this circumstance should be prospectively described in the protocol and supported by disease specific medical literature for the indication. However, it must be acknowledged that both approaches may lead to false positive CR due to limitations of FDG-PET and biopsy resolution/sensitivity.

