### 5.2.1.2 *Secondary Efficacy Endpoints*

The secondary efficacy endpoints are:

- Progression free survival (PFS) of patients treated with CB-839 plus nivolumab. PFS is defined as time from first dose date to the earlier of either progression of disease per RECIST v1.1 or death from any cause.
- Overall survival (OS) of patients treated with CB-839 plus nivolumab. Overall Survival is assessed by time from first dose date to death due to any cause.

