**Table 2 The Censor/Event Rules for Progression Free Survival and Duration of Responsea**

Situation	Date of Event or Censoring	Outcome
No baseline disease assessment	Date of first dose	Censored
No post-baseline assessments and no death	Date of first dose	Censored
No progression and no death	Date of last evaluable tumor assessment	Censored
Additional cancer therapy prior to documentation disease progression or death	Date of last evaluable tumor assessment prior to first new cancer therapy	Censored
Documented RECIST progression per investigator or death within 2 scheduled scan intervals following previous evaluable radiological tumor assessment	First date of evaluation of overall response of PD or death is determined	Event
RECIST progression or death documented to occur after missing 2 scheduled disease assessments (including an overall response of non-evaluable) following previous evaluable radiological tumor assessment	Date of last evaluable tumor assessment with no progression prior to the first of these missed visits	Censored
PD = progressive disease; RECIST = Response Evaluation Criteria in Solid Tumors a RECIST progression or death can occur either on study or during the survival follow up period after treatment discontinuation for symptomatic deterioration, adverse event, or other reason not related to disease and prior to the initiation of new cancer therapy.		

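### Protocol 16.5 counts clinical progression as a PFS event and the SAP does not; the change is unrecorded, protocol 6.1 sides with the SAP, and PFS moves upward relative to 16.5 by an unknown amount.

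*SAP*

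**What the plan says.** Protocol 16.5 runs PFS from Cycle 1 Day 1 to "the date of documented disease progression (radiographic or clinical) or death from any cause, whichever occurs first". Protocol 6.1 lists the same secondary endpoint as PFS per RECIST v1.1 and does not mention clinical progression. Attachment 4 of the protocol adds: "Symptomatic deterioration is not a descriptor of an objective response: it is a reason for stopping study therapy".

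SAP 5.2.1.2 takes "progression of disease per RECIST v1.1 or death from any cause" as the event, and SAP 7.4.2 repeats it as "progression of disease per RECIST 1.1 or death from any cause". The event row of SAP Table 2 reads "Documented RECIST progression per investigator or death within 2 scheduled scan intervals following previous evaluable radiological tumor assessment". A separate row censors "RECIST progression or death documented to occur after missing 2 scheduled disease assessments" at the last evaluable scan before the gap. Other rows censor at the last evaluable scan before new therapy, at the last evaluable scan if neither progression nor death is recorded, and at first dose if there is neither a post-baseline scan nor a death. The table's footnote keeps RECIST progression or death as an event after treatment stops for symptomatic deterioration, provided it precedes new therapy.

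SAP 7.7 records changes to the Cohort 4 reader, Cohort 6, protocol deviations and iRECIST. The PFS event is not among them.

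**The concern.** Patients who stop for clinical deterioration are doing badly when they leave. If they are censored, the Kaplan-Meier estimate treats them as having the same outlook as patients still free of progression. That is informative censoring, and it lifts the curve above what protocol 16.5 would give. Those who do become SAP events later, through a later scan or death, have the event dated later than their clinical progression.

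The plan foresees such patients. Protocol 16.4.3 accepts clinical progression as an alternative to a post-baseline tumor assessment for response evaluability. Protocol 10.6 requires continued imaging only for patients who stop for a reason other than progression or death, without saying whether clinical progression counts as progression there, so scanning may cease. The cohorts are single-arm, so PFS will be read against outside figures with no concurrent control to absorb the shift.

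**Working it through.** The documents give no PFS target, power, event count or rate of clinical-only progression, so there is no stated figure to reproduce. The check traces the rules and then sizes the effect under stated assumptions.

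**Tracing one patient.** Take clinical progression with no RECIST progression at that time.

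| What happens next | Protocol 16.5 | SAP Table 2 |
|---|---|---|
| Later RECIST progression, no new therapy, fewer than two assessments missed | Event at clinical progression | Event, at the later scan |
| Death within two scan intervals of the last evaluable scan, no new therapy | Event at clinical progression | Event, at death |
| New therapy starts first | Event at clinical progression | Censored at last evaluable scan |
| Progression or death after two missed assessments | Event at clinical progression | Censored at last evaluable scan |
| No later RECIST progression or death recorded | Event at clinical progression | Censored at last evaluable scan, or at first dose if no post-baseline scan |

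Scans are every 8 weeks (protocol Attachment 1), so two intervals are 2 × 8 = 16 weeks.

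**Inputs for sizing.** For illustration the underlying median is 4.6 months, the phase 3 nivolumab result cited in protocol 6.3.2.1: 4.6 × 365.25/12/7 = 20.0 weeks. Progression times are taken as exponential. A share c of progressions is clinical only (assumed 5% to 30%) and dated when it occurs; the rest are dated at the next 8-week scan.

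**Upper end in closed form: all clinical-only progressions censored at the last scan.** The chance of passing one interval is q = 2^(−8/20) = 0.758. By week 26 there have been three scans.

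- Protocol 16.5: PFS(26) = (1 − c) × 2^(−24/20) + c × 2^(−26/20) = (1 − c) × 0.4353 + c × 0.4061.
- SAP: hazard per scan h = (1 − c)(1 − q) / [1 − c(1 − q)], and PFS(26) = (1 − h)³.

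At c = 30%: protocol 0.7 × 0.4353 + 0.3 × 0.4061 = 0.427. SAP h = 0.7 × 0.2421 / (1 − 0.3 × 0.2421) = 0.183, and 0.817³ = 0.546. The gain is about 12 points. At c = 5% the same formulas give 0.434 and 0.452, a gain of about 2 points.

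**Range by simulation** (200,000 patients, cutoff at 104 weeks). After clinical progression: median survival 2 or 4 months, 0% to 100% start new therapy, and 0% to 50% get a scan showing RECIST progression. All of these are assumptions.

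| c | 26-week PFS, protocol 16.5 | 26-week PFS, SAP | Gain (points) |
|---|---|---|---|
| 5% | 0.432 | 0.439–0.450 | 0.7–1.8 |
| 10% | 0.433 | 0.447–0.470 | 1.4–3.7 |
| 20% | 0.429 | 0.456–0.504 | 2.7–7.5 |
| 30% | 0.426 | 0.469–0.544 | 4.3–11.8 |

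Between about 30% and 100% of clinical-only progressions were censored. With median survival of 4 months, no new therapy and no scan, about 62% were censored and 38% became events at death. With an underlying median of 2.0 months the gains are smaller: 0.4 to 1.2 points at c = 5% (0.147 against 0.151–0.159) and 3.0 to 9.2 at c = 30% (0.142 against 0.172–0.234).

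**Median.** In continuous time with full censoring the median becomes m/(1 − c): 4.6/0.95 = 4.84, 4.6/0.90 = 5.11, 4.6/0.80 = 5.75 and 4.6/0.70 = 6.57 months. With progression detected only at 8-week scans, the simulated median in the 4.6-month case sat at the 24-week scan (5.52 months) under both rules at c = 5% and 10%. At c = 20% it moved only under full censoring, to 7.36 months. At c = 30% it ranged from 5.52 to 7.36.

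**The case against.** The strongest reply is that the SAP follows the protocol's own endpoint table. Protocol 6.1 specifies RECIST v1.1, and Attachments 4 and 5 both say symptomatic deterioration is not objective progression. RECIST-only PFS is therefore defensible, and the upward shift is measured against one of two conflicting protocol definitions. This stands. It does not remove the conflict with 16.5, which is the detailed analysis definition, and it means the protocol needs reconciling as well as the SAP.

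A reader might infer that every patient who deteriorates without a scan is censored. The documents do not support that. The Table 2 footnote covers symptomatic deterioration explicitly, follow-up imaging is called for after stopping without progression, and deaths within the 16-week window count.

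A reader might also construct a large gap by hand. Suppose that, of 100 patients, 30 have RECIST progression at week 8 and 15 stop earlier for clinical progression with no scan. PFS is then 55/100 = 55% under 16.5 and 1 − 30/85 = 65% with the 15 censored at day 1. That is a worst case. It makes 15/45 = 33% of progressions clinical only and needs all 15 to miss the scan that protocol 10.5 requires at End of Treatment when there is no post-baseline image, with no countable death among them.

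Censoring at new therapy is not a SAP departure in itself, because protocol 16.5 also censors at confounding anticancer therapy. It matters here only because under 16.5 a preceding clinical progression would already have been the event. The two-missed-assessments rule is new in the SAP.

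**Conclusion.** The definitional mismatch is certain from the text, and SAP 7.7 does not disclose it. Relative to protocol 16.5, the SAP rule raised PFS in every scenario examined. Its size cannot be determined from the documents. With 5% to 30% of progressions clinical only and an underlying median of 4.6 months, the rise in 26-week PFS is about 1 to 12 points, and the median may not move at 10% or less. These figures rest on exponential progression times and on assumed scanning, survival and subsequent therapy after clinical progression.

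It would go too far to conclude that the SAP's definition is wrong or that reported PFS will be seriously inflated. PFS is secondary and descriptive, with no test or threshold, and the cohort decision rules rest on response rate. The point is worth correcting but does not threaten the primary analysis.

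**What to change.** 1. Settle one primary PFS definition and state it identically in protocol 6.1, protocol 16.5, SAP 5.2.1.2, SAP 7.4.2 and SAP Table 2. Either choice is workable if it is explicit.
2. Report PFS by cohort under both definitions: RECIST-only as in the present Table 2, and a version counting clinical progression on its recorded date, and deaths after missed scans, as events.
3. Give, by cohort, the number of patients censored after clinical progression, so that the size of the effect can be seen.
4. List the departure from protocol 16.5 in SAP 7.7.

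The cost is some SAP wording and one extra Kaplan-Meier run. One version may show a shorter median. Clinical progression has no stated criteria and is judged by investigators in an open-label study, so its date carries some subjectivity; showing both versions lets the reader weigh that.

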**Table 2 The Censor/Event Rules for Progression Free Survival and Duration of Responsea**

Situation	Date of Event or Censoring	Outcome
No baseline disease assessment	Date of first dose	Censored
No post-baseline assessments and no death	Date of first dose	Censored
No progression and no death	Date of last evaluable tumor assessment	Censored
Additional cancer therapy prior to documentation disease progression or death	Date of last evaluable tumor assessment prior to first new cancer therapy	Censored
Documented RECIST progression per investigator or death within 2 scheduled scan intervals following previous evaluable radiological tumor assessment	First date of evaluation of overall response of PD or death is determined	Event
RECIST progression or death documented to occur after missing 2 scheduled disease assessments (including an overall response of non-evaluable) following previous evaluable radiological tumor assessment	Date of last evaluable tumor assessment with no progression prior to the first of these missed visits	Censored
PD = progressive disease; RECIST = Response Evaluation Criteria in Solid Tumors a RECIST progression or death can occur either on study or during the survival follow up period after treatment discontinuation for symptomatic deterioration, adverse event, or other reason not related to disease and prior to the initiation of new cancer therapy.		

